4.7.6. Safety ECG Measurements, Physical Examinations, Vital Signs, Pregnancy Testing

Safety ECG Measurements, Physical Examinations, Vital Signs, and Pregnancy Testing will be provided as by-participant listings.

4.8. Other Analyses

4.8.1. Pharmacokinetics Analysis

PK concentrations and PK parameters will be summarized descriptively based on the PK Analysis Set and presented by treatment and cohort. Other PK analyses will not be covered by this SAP.

For PK concentration data, values reported below the quantitation limit (BQL) will not be imputed in summary statistics with only the number of participants who have non-missing quantifiable results included at each time point. Any positive concentration (i.e., greater than LLOQ) is excluded from the summary statistics at the Day 1 pre-dose visit only.

For PK parameters estimation, samples BQL prior to the first quantifiable concentration will be set to a concentration value of zero, and BQL values that occur after the first quantifiable point will be considered as missing data.

If a missing value is reported due to no valid or missing sample result in the summary of concentration data and PK parameters, it will be presented as not reported “NR” and excluded from PK analyses and not imputed at any time points.

The actual reported values will be provided in individual participant listings.

4.8.1.1. PK Variables

PK variables include individual concentration measurements for VIR-2218, its metabolite AS(N-1)3'VIR-2218, and VIR-3434 following the collection times provided in the protocol, and the estimated PK parameters in evaluation of PK objectives including but not be limited to, C_{\max} (maximum observed concentration of drug following a dose), $C_{\tau_{au}}$ (concentration at dosing time plus T_{au}), $AUC_{\tau_{au}}$ (area under the concentration-time curve during the dose interval), and $t_{1/2}$ (terminal elimination half-life).

Participants' data collected from the VIR-3434 PK sub-study will be included in all analysis. The details of the VIR-3434 PK sub-study can be found in the Protocol.

4.8.1.2. Analysis of PK Concentrations

Plasma concentrations of VIR-2218 and its metabolite AS(N-1)3'VIR-2218 and serum concentrations of VIR-3434 will be listed and summarized by the nominal sampling time using descriptive statistics (n, mean, SD, coefficient of variation [CV%], median, min, max, geometric mean, and Geometric CV% [GeoCV%]). Geometric CV% will be calculated using the following formula where SD is the standard deviation of the log-transformed data: $\text{GeoCV\%} = \text{sqrt}[(\exp(\text{SD}^2) - 1)] \times 100$. Participants' data collected from the VIR-3434 PK sub-study will be marked.

Anomalous concentrations identified as sampling errors by the clinical pharmacologist will be excluded from summaries but flagged in the listings.

Both individual and aggregate mean (\pm SD) of the serum concentrations of free VIR-3434 will be displayed graphically in linear and semi-logarithmic plots of concentration versus time. Time will be displayed in units of days of time elapsed relative to dosing, with dosing at time zero (clinical Day 1). The nominal sample collection timepoints will be used for plots. The number of participants with quantifiable concentrations per timepoint will be displayed in each plot of mean concentrations. Mean post-dose concentration values that are BQL will not be displayed in the figures and the remaining points will be connected.

4.8.1.3. Analysis of PK Parameters

PK parameter summaries for free VIR-3434 serum concentrations will include all participants for whom PK parameters can be derived. The sample size for each PK parameter will be based on the number of participants with non-missing data for that PK parameter.

Individual participant PK parameters for VIR-3434 will be listed and summarized using descriptive statistics (n, mean, SD, CV%, median, min, max, geometric mean, and GeoCV%).

Selected summary statistics (e.g., geometric mean with GeoCV% or median with min and max) for PK parameters will be presented by cohort.

4.8.2. Immunogenicity Analysis

All immunogenicity analyses described in this section will be based on the Immunogenicity Analysis Set and presented by cohort.

4.8.2.1. Definition of Variables

The immunogenicity analysis will be analyzed through the following ADA to VIR-3434 variables:

- Binding ADA: binding ADA is defined as any antibodies (neutralizing and non-neutralizing) binding biologic drug, which is determined by the positive results from both screening and confirmed test using an *in vitro* test method. Any positive screening result followed by a confirmed negative result will be treated as a negative response.
- Titers: the presence and quasi-quantitative expression of the level of ADA, which is determined by serially diluting the serum fraction of blood and assaying (testing) each dilution for the antibody of interest
- Treatment-induced ADA: defined as a baseline sample negative for ADA (or missing) and a post-baseline sample confirmed positive for ADA.
- Treatment-boosted ADA: defined as pre-existing ADA (confirmed positive at baseline) that is boosted to $> 4x$ baseline ADA titer at any post-baseline measures.
- Treatment-unaffected ADA: defined as pre-existing ADA (confirmed positive at baseline) that is changed to negative or increased to $\leq 4x$ baseline ADA titer at all post-baseline measures.
- Transient ADA: ADA is defined as transient if the last ADA result for a participant is negative but there is treatment-induced ADA at only one time point (excluding the last non-missing result) or there are ≥ 2 samples with treatment-induced ADA with fewer than 16 weeks between the first and last samples that are positive for ADA (irrespective of negative samples in between).
- Persistent ADA: ADA is defined as persistent if there are ≥ 2 samples at different timepoints with treatment-induced ADA with 16 or more weeks between the first and the last samples that are positive for ADA, or there is treatment-induced ADA at the final timepoint.

4.8.2.2. Analysis Methods

The incidence rate of participants who had samples of negative, screened positive, and confirmed positive for binding ADA to VIR-3434 will be summarized using frequency counts and percentages at baseline and each post-baseline visit up to EOS. Titers for participants confirmed positive for ADA to VIR-3434 will be summarized descriptively (n, median, min, max).

A summary table of immunogenicity results will be provided, including the number of study participants with:

- Any ADA result

- Both baseline and post-baseline ADA
- Any baseline ADA
- Any post-baseline ADA

The number and percentage of participants (based on the participants with any post-baseline ADA) in each of the following ADA type categories will be provided. In addition, titers for participants with ADA to VIR-3434 will also be summarized descriptively (n, median, min, max) for ADA types, including treatment-induced ADA, treatment-boosted ADA, and treatment-unaffected ADA.

- Treatment-emergent ADA (treatment-induced or treatment-boosted)
- Treatment-induced ADA
- Treatment-boosted ADA
- Treatment-unaffected ADA

For transient or persistent ADA to VIR-3434, the number and percentage of participants (based on the participants with any post-baseline ADA) will be summarized. Titers for participants with transient or persistent ADA to VIR-3434 will also be summarized using descriptive statistics (n, median, min, max).

An individual participant listing will be provided by participant ID, visit in chronological order.

4.9. Interim Analyses

4.9.1. Introduction

[figure not shown]
CCI

A large black rectangular redaction box covers the majority of the page content below the 'CCI' label, starting from the 'Introduction' section and extending down to the 'General Consideration' section.

4.9.2. General Consideration

For each planned IA, the VIR Biometrics team and a designated CRO will prepare the analysis package and conduct the analysis using cleaned data up to the IA data cutoff date. All data reported on or before the data cutoff date will be included in the IA. General considerations, reporting conventions, and analysis methods specified for the final analysis apply to IA, unless otherwise specified.

CCI

A smaller black rectangular redaction box covers the bottom portion of the page content below the 'General Consideration' section.

4.9.3. Interim Analysis 1

CCI

4.9.3.1. Subject Disposition

The number of participants in the following categories will be summarized:

- All Enrolled Set
- iFAS1
- iSAS1

The number and percentage of study participants (based on the All Enrolled Set) in each of the following disposition categories will be summarized by cohort and overall:

- Participants completed Week 24 visit
- Participants early withdrawn from the study
 - Primary reason for early withdrawal from study
- Roll over from/to other study/sub-study

A by-participant listing will be provided for disposition, including primary reasons for premature discontinuation of VIR-3434/ TDF/TD/ VIR-2218/ PEG-IFN α .

4.9.3.2. Demographics and Baseline Characteristics

The same demographics and baseline characteristics specified in [Section 4.2.2](#) will be summarized based on the All Enrolled Set.

4.9.3.3. Medical History, Prior/Concomitant Medications and Concomitant Procedure

Medical History, Prior/Concomitant Medications and Concomitant Procedure specified in [Section 4.2.3](#) and [Section 4.2.4](#) will be summarized based on the iFAS1.

4.9.3.4. Extent of Exposure and Study Intervention Compliance

For the IA1 purpose, the study drug exposure and study intervention compliance will be calculated using the same approach specified in [Section 4.7.1](#) based on the iSAS1 and [Section 4.7.2](#) based on the iFAS1, respectively. For other cohorts, if participants are still on a study intervention at the IA1 data cutoff date, the IA1 data cutoff date will be used as the last exposure date for the exposure calculation.

4.9.3.5. Efficacy Analysis

All efficacy analyses described in this section will be based on the iFAS1.

4.9.3.5.1. Primary Endpoint Analysis

No primary endpoint(s) analysis will be conducted for IA1.

The observed values of the parameters related to the primary endpoint, i.e., HBV DNA and HBsAg and the absolute changes from baseline values in both IU/mL and \log_{10} IU/mL at each visit up to the IA1 data cutoff date will be summarized using descriptive statistics (n, mean, SD, median, Q1, Q3, min, max) by cohort. The observed value at the nadir of HBsAg and the maximum change from baseline will be included in the HBsAg descriptive statistics summary table.

4.9.3.5.2. Secondary Endpoints Analysis

For IA1, the secondary endpoints analysis will be performed as described in [Section 4.4.1](#), including the endpoints below:

- Serum HBsAg levels and change from baseline across timepoints in the study
- Serum HBsAg level at nadir during the study
- Time to achieve serum HBsAg loss
- For HBeAg-positive participants: proportion of participants with HBeAg loss (undetectable HBeAg) and/or anti-HBe seroconversion
- Mean change in serum HBsAg level from baseline across timepoints in the study
- Proportion of participants achieving HBV DNA < LLOQ across timepoints in the study
- Incidence and titers of ADA (if applicable) to VIR-3434
- Proportion of participants achieving ALT \leq ULN across timepoints in the study

4.9.3.5.3. Exploratory Endpoints Analysis

For IA1, the following Exploratory Endpoints will be analyzed as described in [Section 4.5.1](#):

- HBV RNA and HBcrAg levels and change from baseline across timepoints in the study
- HBV DNA levels and change from baseline across timepoints in the study
- Nadir and maximum change of HBV DNA level from baseline in the study

4.9.3.6. Safety Analysis

For IA1, the safety analyses specified in [Section 4.7.3](#) to [Section 4.7.6](#) will be performed based on the iSAS1.

4.9.4. Interim Analysis 2

CCI

CCI

4.9.4.1. Subject Disposition

The number of participants in the following categories will be summarized:

- All Enrolled Set
- iFAS2
- iSAS2

The number and percentage of study participants (based on the All Enrolled Set) in each of the following disposition categories will be summarized by cohort and overall:

- Participants completed EOT visit
- Participants early withdrawn from the study
 - Primary reason for early withdrawal from study
- Roll over from/to other study/sub-study

A by-participant listing will be provided for disposition, including primary reasons for premature discontinuation of VIR-3434/ TDF/TD/ VIR-2218/ PEG-IFN α .

4.9.4.2. Demographics and Baseline Characteristics

The same demographics and baseline characteristics specified in [Section 4.2.2](#) will be summarized based on the All Enrolled Set.

4.9.4.3. Medical History, Prior/Concomitant Medications and Concomitant Procedure

Medical History, Prior/Concomitant Medications and Concomitant Procedure specified in [Section 4.2.3](#) and [Section 4.2.4](#) will be summarized based on the iFAS2.

4.9.4.4. Extent of Exposure and Study Intervention Compliance

For the IA2 purpose, the study drug exposure and study intervention compliance will be calculated using the same approach specified in [Section 4.7.1](#) based on the iSAS2 and [Section 4.7.2](#) based on the iFAS2, respectively. For other cohorts, if participants are still on a study intervention at the IA2 data cutoff date, the IA2 data cutoff date will be used as the last exposure date for the exposure calculation.

4.9.4.5. Efficacy Analysis

All efficacy analyses described in this section will be based on the iFAS2.

4.9.4.5.1. Primary Endpoint Analysis

For IA2, the proportion of participants achieving suppression of HBV DNA (< LLOQ) with HBsAg loss (< 0.05 IU/mL) at EOT will be summarized, and the two-sided 95% exact Clopper-Pearson CIs will be calculated for each cohort.

4.9.4.5.2. Secondary Endpoints Analysis

For IA2, the secondary endpoints analysis will be performed as described in [Section 4.4.1](#), including the endpoints below:

- Proportion of participants with serum HBsAg \leq 10 IU/mL at EOT
- Proportion of participants with HBsAg loss with anti-HBs seroconversion at EOT
- Proportion of participants achieving HBsAg loss (< 0.05 IU/mL) at EOT
- Serum HBsAg levels and change from baseline across timepoints in the study
- Serum HBsAg level at nadir during the study
- Mean change in serum HBsAg level from baseline across timepoints in the study
- Time to achieve nadir of serum HBsAg during the study
- Time to achieve serum HBsAg loss (< 0.05 IU/mL)
- For HBeAg-positive participants: proportion of participants with HBeAg loss (undetectable HBeAg) and/or anti-HBe seroconversion
- Proportion of participants achieving HBV DNA < LLOQ across timepoints in the study
- Proportion of participants achieving ALT \leq ULN across timepoints in the study

4.9.4.5.3. Exploratory Endpoints Analysis

Data collected based on CLDQ-HBV and WPAI questionnaires will be analyzed as described in [Section 4.5.2](#) based on iFAS2:

- Change from baseline in health-related quality of life as measured by the CLDQ-HBV questionnaire
- Change from baseline in work productivity and daily activities as measured by the WPAI questionnaire

4.9.4.6. Safety Analysis

Safety analyses specified in [Section 4.7.3](#) to [Section 4.7.6](#) will be performed based on the iSAS2.

4.9.5. Interim Analysis 3

CCI

4.9.5.1. Subject Disposition

The number of participants in the following categories will be summarized:

- All Enrolled Set
- iFAS3
- iSAS3

The number and percentage of study participants (based on the All Enrolled Set) in each of the following disposition categories will be summarized by cohort and overall:

- Participants who completed all study interventions
- Participants who met NRTI (TDF/TD) discontinuation criteria
- Participants who met NRTI (TDF/TD) retreatment criteria
- Participants early withdrawn from the study
 - Primary reason for early withdrawal from study
- Roll over from/to other study/sub-study

A by-participant listing will be provided for disposition, including primary reasons for premature discontinuation of VIR-3434/ TDF/TD/ VIR-2218/ PEG-IFN α .

4.9.5.2. Demographics and Baseline Characteristics

The same demographics and baseline characteristics specified in [Section 4.2.2](#) will be summarized based on the All Enrolled Set.

4.9.5.3. Medical History, Prior/Concomitant Medications and Concomitant Procedure

Medical History, Prior/Concomitant Medications and Concomitant Procedure specified in [Section 4.2.3](#) and [Section 4.2.4](#) will be summarized based on the iFAS3.

4.9.5.4. Extent of Exposure and Study Intervention Compliance

For the IA3 purpose, the study drug exposure and study intervention compliance will be calculated using the same approach specified in [Section 4.7.1](#) based on the iSAS3 and [Section 4.7.2](#) based on the iFAS3, respectively. For other cohorts, if participants are still on a study intervention at the IA3 data cutoff date, the IA3 data cutoff date will be used as the last exposure date for the exposure calculation.

4.9.5.5. Efficacy Analysis

All efficacy analyses described in this section will be based on iFAS3.

4.9.5.5.1. Secondary Endpoints Analysis

For IA3, the secondary endpoints analysis will be performed as described in [Section 4.4.1](#), including the endpoints below:

- Proportion of participants with serum HBsAg \leq 10 IU/mL at 24 weeks post-EOT
- Proportion of participants with HBsAg loss with anti-HBs seroconversion at 24 weeks post-EOT

- Proportion of participants achieving HBsAg loss (< 0.05 IU/mL) at 24 weeks post-EOT
- Serum HBsAg levels and change from baseline across timepoints in the study
- Serum HBsAg level at nadir during the study
- Mean change in serum HBsAg level from baseline across timepoints in the study
- For HBeAg-positive participants: proportion of participants with HBeAg loss (undetectable HBeAg) and/or anti-HBe seroconversion
- Proportion of participants achieving HBV DNA (< LLOQ) across timepoints in the study
- Proportion of participants achieving ALT \leq ULN across timepoints in the study
- Proportion of participants achieving sustained suppression of HBV DNA (< LLOQ) with HBsAg loss (< 0.05 IU/mL) at 24 weeks after discontinuation of all treatment
- Proportion of participants achieving sustained suppression of HBV DNA (< LLOQ) at 24 weeks after discontinuation of all treatment

4.9.5.6. Safety Analysis

Safety analyses specified in [Section 4.7.3](#) to [Section 4.7.6](#) will be performed based on iSAS3.

4.10. Modifications

Not applicable.

4.10.1. Modifications to the Approved Study Protocol

Protocol	SAP v2.0

Section 3: secondary endpoints:
 
9. Proportion of participants achieving sustained suppression of HBV DNA (< LLOQ) with HBsAg loss (< 0.05 IU/mL) after discontinuation of all treatment:
 
 a. at 24 weeks b. at the F48 Follow-Up visit 
11. Proportion of participants achieving sustained suppression of HBV DNA (< LLOQ) after discontinuation of all treatment:
 
 a. at 24 weeks b. at the F48 Follow-Up visit 	
A modification to the timepoint is below due to early study termination:
 
 a. at 24 weeks post-stopping all treatments b. at the last Follow-Up visit, for participants who have > 24 weeks of discontinuation post-stopping all treatments c. at the last Follow-Up visit 
Add additional analysis below:
 
In addition, the number and percentage of participants achieving

	
 • sustained suppression of HBV DNA (< LLOQ), allowing transient viremia after discontinuation of all treatment • sustained suppression of HBV DNA (< LLOQ) with HBsAg loss (< 0.05 IU/mL), allowing transient viremia after discontinuation of all treatment 
where transient viremia is defined as HBV DNA \geq LLOQ or HBsAg \geq LLOQ for \leq 35 days, adapted from the 2022 American Association for the Study of Liver Diseases (AASLD) – The European Association for the Study of the Liver (EASL) functional cure definition (AASLD-EASL, 2022), will be analyzed similarly.
 
The analyses above will be repeated after replacing “HBsAg loss (<0.05 IU/mL) with “HBsAg < 100 IU/mL”. Accordingly, the transient viremia is defined as HBV DNA \geq LLOQ or HBsAg \geq 100 IU/mL for \leq 35 days.

Master protocol Section 9.3: All Screened Set includes all participants who signed the informed consent form.	All Screened Set will not be included in this SAP. Because the All Screened Set will not be used in the analysis. Instead, the number of participants screened will be provided in the disposition table.
Section 9.4.1: TEAE definition for this sub-protocol: An AE that is reported with an onset date on or after the start of study intervention(s) until end of Follow-Up Period.	TEAE is defined as any AEs reported with an onset date on or after the first dose of study intervention(s) until the end of TE Period. The TE Period is defined as the time period on or from the start of study intervention(s) until the last dose of VIR-2218 + 30 days, or VIR-3434 + 24 weeks, or PEG-IFN α + 30 days, or TDF/TD + 30 days, whichever is later.
Protocol Section 9.5: Three interim analyses will be conducted for each cohort to evaluate the efficacy endpoints at Week 24, EOT, and 24 weeks post-EOT when all participants in the cohort completed the respective visits.	The Sponsor has decided to combine IA1 and IA2. As the study will be terminated earlier, the Sponsor also plans to merge IA3 with the final analysis.

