9.4. Statistical Analyses

9.4.1. General Considerations

Refer to the Master Protocol.

TEAE definition for this sub-protocol: An AE that is reported with an onset date on or after the start of study intervention(s) until end of Follow-Up Period.

Prior to the final analysis, interim analyses will be conducted, and the analyses may be submitted for publication or to regulatory agencies to seek guidance for the overall clinical development program.

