1.2.3. Intervention Groups and Duration

There are 5 cohorts planned in this sub-study.

Table 3: Intervention Groups

Cohort	Study Drug	Dose	Route	Number of Doses	Frequency of Dosing
1a	VIR-3434	300 mg	SC	12	Every 4 weeks
	TDF	300 mg ^b	Oral	\geq 308 ^c	Every day
2a	VIR-3434	Up to 300 mg ^a	SC	12	Every 4 weeks
	TDF	300 mg ^b	Oral	\geq 308 ^c	Every day
3a	VIR-3434	300 mg	SC	4-6 ^d	Every 8-12 weeks ^d
	TDF	300 mg ^b	Oral	\geq 252 ^c	Every day
4a	VIR-3434	300 mg	SC	12	Every 4 weeks
	VIR-2218	200 mg	SC	12	Every 4 weeks
	TDF	300 mg ^b	Oral	\geq 308 ^c	Every day
5a	VIR-3434	300 mg	SC	13	Every 4 weeks
	VIR-2218	200 mg	SC	13	Every 4 weeks
	PEG-IFN α	180 mcg	SC	48	Every week
	TDF	300 mg ^b	Oral	\geq 336 ^c	Every day

^a The dose of VIR-3434 will be determined before participants are enrolled in the cohort.

^b Tenofovir disoproxil fumarate dose (TDF) will be 300 mg as approved by the FDA. Supply outside the United States may be Tenofovir disoproxil (TD) 245 mg.

^c The minimum number of doses received by participant. Participants will continue receiving additional doses of TDF until they qualify for NRTI discontinuation.

^d The dosing regimen will be finalized before participants are enrolled in the cohort.

The total duration in the study for participants will be up to 100 weeks in cohorts 1a, 2a, and Cohort 4a, 92-96 weeks for Cohort 3a, and 104 weeks for Cohort 5a. This includes a Screening Period (up to 56 days or 8 weeks), Treatment Period (44 weeks for cohorts 1a and 2a, 36 or

40 weeks for Cohort 3a, 44 weeks for Cohort 4a, and 48 weeks for Cohort 5a) and a Follow-Up Period (up to 48 weeks) for all cohorts.

Once participants complete the Treatment Period per their respective cohort, they will enter the Follow-Up Period. Participants will discontinue the NRTI at the F1 or F12 visit in the Follow-Up Period if they meet the criteria to discontinue NRTI ([Section 1.2.4](#)) based on the data available. Additional study visits are required for participants who discontinue NRTI in the Follow-Up Period as indicated in the SOA in the study protocol. Participants who discontinue NRTI at F1 visit will be required to return to the site for additional visits at F2, F6, F10, F28, F32, F40, and F44. Participants who discontinue NRTI at F12 visit will be required to return to the site for additional visits at F14, F18, F22, F28, F32, F40, and F44.

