1.2.4. NRTI Discontinuation

Participants will discontinue NRTI at F1 or at F12 Follow-Up visits based on the most recent data available if they meet all of the following criteria:

- HBsAg < LLOQ
- Suppressed HBV DNA (defined as < LLOQ)
- Undetectable HBeAg (based on quantitative HBeAg)
- ALT \leq 2 times the upper limit of normal (ULN).

Participants who meet the criteria to discontinue NRTI treatment will continue to be followed? per the Follow-Up Period SOA. Participants who meet NRTI discontinuation criteria but are not appropriate for NRTI discontinuation due to other reasons, based on the opinion of the Investigator, may continue on NRTI treatment following discussion with the Sponsor Medical Monitor to document the rationale for continuing NRTI.

Participants who do not qualify for NRTI discontinuation will continue taking the NRTI until the end of the Follow-Up Period. Once a participant has completed the study, long-term care should be determined by the Investigator or primary treating physician based on local clinical guidelines.

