For event/measurement occurring on or after Day 1, the study day will be calculated as:

$$\text{Study Day} = (\text{Date of event/measurement} - \text{Date of first study drug administration}) + 1.$$

End of treatment (EOT) date: EOT date is the date of the last dose of VIR-2218, VIR-3434 and PEG-IFNa.

EOT assessment: The earliest available assessment on or after EOT date.

EOT + 24 weeks assessment: The earliest available assessment on or after EOT + 161 days.

Treatment Period and Follow-Up Period: Treatment Period and Follow-Up Period are defined in the protocol.

Treatment-emergent (TE) Period: The TE Period is defined as the time period on or from the start of study intervention(s) until the last dose of VIR-2218 + 30 days, or VIR-3434 + 24 weeks, or PEG-IFN α + 30 days, or TDF/TD + 30 days, whichever is later. The TE Period will be used for safety analysis.

Post-TE Period: The Post-TE Period is defined as the time period after the TE Period through the end of Follow-Up Period.

Analysis windows: The analysis window rules for protocol-defined visits are provided in [Appendix 2](#).

Unscheduled visits: Unscheduled visit measurements will be included in the analysis as follows:

1. In planned visit windows as specified, the analysis window rules described in [Appendix 2](#), if applicable.
2. In the derivation of the baseline.
3. In the derivation of maximum and minimum values, or maximum and minimum change from baseline values during the Treatment Period and Follow-Up Period for efficacy analyses, or worst values/grades during the TE Period for safety analyses.
4. In individual participant data listings as appropriate.

Repeated observations: Measurements recorded at different time points are defined as repeated observations. If an assessment has planned repeated measurements, then statistical summaries will present all planned time points, as appropriate.

If there are multiple records at a single assessment date, regardless of whether scheduled or unscheduled visit, the latest record will be used for the analysis.

Missing data handling conventions:

- Missing data can occur due to study withdrawal or participants lost to follow-up before the completion of the study or due to intermittent missing values (i.e., data between two non-missing assessments).
- Missing data in the by-participant data listings will be presented as missing.

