4.7.3. Adverse Events (AEs)

For analysis purposes, AEs will be classified as pre-treatment AEs, TEAEs, and post-TE AEs, defined as follows:

- Pre-treatment AE: defined as any AEs that started after informed consent was signed and prior to the administration of the study intervention.
- TEAE: defined as any AEs reported with an onset date on or after the first dose of study intervention(s) until the end of TE Period.
- Post-TE AE: defined as any AEs with onset after the TE Period through the end of Follow-Up Period.

All AEs will be coded using MedDRA version 25.0 and later.

For AEs with completely missing or partially missing start/stop dates, if it can't be decided whether the AE is TEAE due to the missing dates, the AE will be classified as TEAE. Imputation rules for missing or partial missing dates of AEs are described in [Appendix 4](#).

An overview table of all TEAEs by cohort and overall will be summarized in the following categories:

- Number of TEAEs (total number of TEAEs only)
- Participants with any TEAEs
- Participants with TEAEs by strongest relationship to study intervention(s)
- Participants with TEAEs by maximum severity
- Participants with TEAEs leading to any study intervention discontinuation
- Participants with TEAEs leading to any study intervention interruption
- Participants with TEAEs leading to PEG-IFNa and TDF/TD dose reduction
- Participants with study intervention-related TEAEs
- Participants with Grade 3/4/5 TEAEs
- Participants with serious TEAEs
- Participants with study intervention-related serious TEAEs
- Participants with TEAE leading to death

The following summary tables of TEAEs will be presented by MedDRA SOC and PT using the number and percentage of participants by cohort and overall:

- TEAEs
- Study intervention related TEAEs
- TEAEs by maximum severity
- Serious TEAEs

In addition, the following TEAE tables will also be summarized by MedDRA PT only for each cohort and overall:

- TEAEs
- Study intervention related TEAEs
- Serious TEAEs

A participant with multiple occurrences of the same AE will be counted only once, at the maximum severity (toxicity grade) or strongest relationship to study intervention.

A TEAE table of injection site reactions will be summarized by MedDRA PT for each cohort and overall in order of descending incidence.

The following table-listings will be presented per cohort based on the All Enrolled Set:

- SAEs
- AEs leading to study intervention interruption

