4.7.4.2. Summaries of Laboratory Abnormalities

The Common Terminology Criteria for Adverse Events (CTCAE) v5.0 (CTCAE 5.0 2017) will be used as the reference on the grading scale to assign severity (toxicity) grades (1 to 4) to abnormal results for the laboratory parameters of interest, as shown in [Appendix 5](#). Grade 0 refers to the normal values that do not meet the criteria of laboratory abnormalities. Grade 5 refers to death related to an adverse event, if any.

For the laboratory abnormalities, the number and percentage of participants who met at least 1 threshold criterion of severity grade during the TE Period will be summarized by cohort based on the most severe post-baseline abnormality for selected laboratory parameters in [Appendix 5](#).

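### In the STRIVE SAP, AE-incidence and worst-lab-grade tables stop about 24 weeks after EOT for participants taken off NRTI and not retreated, but run to the end of follow-up for those who stay on NRTI

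*SAP*

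**What the plan says.** SAP 4.10.1 lists the TEAE definition among its departures from the protocol. The protocol wording it cites counts onset through the end of follow-up. The protocol supplied here is for the sister sub-study THRIVE, and its Section 9.4.1 reads the same way: "An AE that is reported with an onset date on or after the start of study intervention(s) until end of Follow-Up Period". The SAP substitutes onset "on or after the first dose of study intervention(s) until the end of TE Period". Other rows of that table explain themselves (early termination, an analysis set that is not used); this one does not.

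SAP 4.1 runs the TE Period from the start of study intervention "until the last dose of VIR-2218 + 30 days, or VIR-3434 + 24 weeks, or PEG-IFN α + 30 days, or TDF/TD + 30 days, whichever is later". SAP 4.7 makes the TE Period the default data scope for safety. In SAP 4.7.3 every AE-incidence table is a TEAE table. The section also defines a further class, "Post-TE AE: defined as any AEs with onset after the TE Period through the end of Follow-Up Period", but assigns it no summary table. SAP 4.7.4.2 counts participants "who met at least 1 threshold criterion of severity grade during the TE Period".

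Three design facts determine how the rule acts:
- SAP 1.2.3 plans a "Follow-Up Period (up to 48 weeks) for all cohorts".
- In SAP 4.1, "EOT date is the date of the last dose of VIR-2218, VIR-3434 and PEG-IFNa"; TDF/TD plays no part in that date.
- Under SAP 1.2.4, "Participants will discontinue NRTI at F1 or at F12 Follow-Up visits" if they meet four criteria on HBsAg, HBV DNA, HBeAg and ALT. Those who do not qualify take NRTI to the end of follow-up.

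**The concern.** Because TDF/TD is one of the drugs that sets the cut-off, a participant's safety window depends on whether NRTI was stopped, and stopping depends on efficacy response. The window is shortest for the participants who go through NRTI withdrawal. A cohort-level TEAE percentage then pools people observed for different lengths of follow-up, with no participant-time denominator.

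The design itself treats the omitted interval as worth watching. SAP 1.2.3 adds visits at F28, F32, F40 and F44 specifically for participants who stop NRTI, and the retreatment criteria in SAP 1.2.5 apply throughout follow-up. SAP 4.1 splits the efficacy summaries by TDF/TD discontinuation; no matching safety summary is planned.

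**Working it through.** The documents give no figure for the share of follow-up inside the TE Period. The follow-up length can be checked against the stated study durations in SAP 1.2.3 (screening + treatment + follow-up, weeks): 8 + 44 + 48 = 100 for Cohorts 1a, 2a and 4a; 8 + 36 + 48 = 92 or 8 + 40 + 48 = 96 for Cohort 3a; 8 + 48 + 48 = 104 for Cohort 5a. All agree, so planned follow-up is 48 weeks = 336 days.

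**Cut-off.** Count days from EOT and let L be the day of the last TDF/TD dose. Assume VIR-3434 was given through EOT. The VIR-2218 and PEG-IFNα rules give at most EOT + 30 d and cannot be the latest. So

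TE end = max(168, L + 30), capped at 336.

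F1 is about EOT + 7 d and F12 about EOT + 84 d.

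| NRTI course, no retreatment | TE end | Follow-up days omitted | Off-NRTI days | Omitted share of off-NRTI time |
|---|---|---|---|---|
| Stopped at F1 | max(168, 37) = 168 | 336 − 168 = 168 | 336 − 7 = 329 | 168/329 = 51% |
| Stopped at F12 | max(168, 114) = 168 | 336 − 168 = 168 | 336 − 84 = 252 | 168/252 = 67% |
| Continued to F48 | max(168, 366), capped at 336 | 0 | 0 | – |

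Under the protocol definition all three rows would cover 336 of 336 days. The scheduled visits after day 168 are F28, F32, F36, F40, F44 and F48.

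**Retreatment.** TDF/TD sets the cut-off only when L + 30 > 168, that is, L > 138. If retreatment doses count and a retreated participant takes TDF/TD to the end of follow-up, TE end reaches 336 and the earlier off-NRTI interval comes back into the tables. The SAP does not state whether they count.

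**Outputs cut at the TE Period, and outputs that are not:**

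| Output | Scope in the SAP |
|---|---|
| AE-incidence tables, including related and serious TEAEs (4.7.3) | TE Period |
| Worst lab grade per participant (4.7.4.2) | TE Period |
| Lab values by visit (4.7.4.1) | to EOS |
| ECI by visit (4.7.5) | to EOS |
| ALT ≤ ULN and HBV DNA < LLOQ by visit (4.4.1) | across study visits |
| Virological relapse; meeting NRTI retreatment criteria (4.5.1) | during the study |
| Table-listings of SAEs and of AEs leading to interruption, discontinuation or death (4.7.3) | no TE limit written |
| Listing of all AEs (4.7.3) | no TE limit written |
| SAE part of secondary endpoint 1 (4.4.2) | no TE limit written, but 4.7 sets a TE default |

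**The case against.** A reader might infer that late off-treatment events never reach a table, or that late hepatic events appear only in listings. The documents do not support either. ECIs, liver function tests and coagulation are summarised by visit to EOS, ALT normalisation is tabulated by visit, and relapse and retreatment are counted. SAP 4.7.5 does label the ECIs as TE events, but it explicitly runs their summary to EOS, and I read that as controlling. SAEs and fatal AEs reach table-listings, which can be read through in cohorts of about 10 or 15.

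Other points on the sponsor's side:
- **A drug-based window is a recognised choice.** With the VIR-3434 half-life of about 25 days given in Protocol 4.3.1, 24 weeks is 168/25 = 6.7 half-lives. A participant still on TDF/TD is still exposed to study drug. The change is also openly declared. This defends having a TE table; it does not explain why nothing covers the time after it.
- **No stopper-versus-continuer comparison of AEs is planned.** AE tables are by cohort and overall. That is correct, so a reading that the SAP plans a biased comparison goes too far. The unequal windows still sit inside each pooled percentage.
- **Retreatment may recapture those who relapse.** SAP 1.2.1 equates NRTI with TDF/TD in STRIVE, which favours this reading. It would help those participants, but it adds a second way in which outcome sets the window.
- **Early termination.** SAP 4.10.1 says the study will end early, so the percentages are planned maxima.
- **Scope.** In THRIVE, TDF stops with the last VIR-3434 or VIR-2218 dose for everyone (Protocol 4.3.3), so the contrast by NRTI status is confined to STRIVE.

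These points narrow the gap. The ECI covers ALT only, and by-visit statistics do not give a participant's worst grade for AST, bilirubin, albumin or INR.

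**Conclusion.** The point stands in a limited form. For STRIVE participants who stop NRTI at F1 or F12 and are not retreated, AE-incidence and worst-lab-grade tables end at about EOT + 24 weeks and omit up to 168 of 336 planned follow-up days. That is at most 51% of off-NRTI time for an F1 stop and 67% for an F12 stop. For those who stay on NRTI nothing is omitted.

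Three things lack a summary after the cut-off: the incidence of AEs outside the separately listed categories, participant-level worst lab grade, and a count of late SAEs. The last is uncertain, because endpoint 1 names SAEs without a TE limit while the Section 4.7 default and the serious-TEAE tables point the other way.

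The figures assume VIR-3434 dosing through EOT, the full 48-week follow-up, nominal visit days and no retreatment. The number of participants affected cannot be derived from the documents. This is a worthwhile, inexpensive improvement to the safety reporting; it does not affect the primary efficacy analysis.

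**What to change.** 1. Keep the TE Period tables as the drug-exposure view.
2. Add AE, SAE, related-AE and worst-lab-grade tables from first dose to the end of follow-up, which is the protocol's own definition.
3. Add a post-TE/off-NRTI summary by NRTI status, giving participant-weeks at risk so that unequal observation is visible.
4. State whether TDF/TD given as retreatment counts as the last dose that sets the TE Period.
5. State whether the SAE part of secondary endpoint 1 is limited to the TE Period.
6. Give the reason for the changed TEAE definition in SAP 4.10.1.

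The cost is a few repeat tables with a different date cut, using data already collected. The drawback is that a longer window admits more events unrelated to study drug; keeping the TE tables alongside lets a reader see both.
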